10.1 Confidentiality

All laboratory specimens, evaluation forms, reports, and other records will be identified in a manner designed to maintain subject confidentiality. All records will be kept in a secure storage area with limited access. Clinical information will not be released without the written permission of the subject (or the subject's legal guardian), except as necessary for monitoring and auditing by the sponsor, its designee, the US FDA, or the IRB/IEC.

The investigator and all employees and coworkers involved with this study may not disclose or use for any purpose other than performance of the study any data, record, or other unpublished, confidential information disclosed to those individuals for the purpose of the study. Prior written agreement from the sponsor or its designee must be obtained for the disclosure of any said confidential information to other parties.

10.2 Financial Disclosure and Obligations

Investigators are required to provide financial disclosure information to allow the sponsor to submit the complete and accurate certification or disclosure statements required under 21 Code of Federal Regulations (CFR) 54. In addition, the investigator must provide to the sponsor a commitment to promptly update this information if any relevant changes occur during the course of the investigation and for 1 year following the completion of the study.

Neither the sponsor nor PPD is financially responsible for further testing or treatment of any medical condition that may be detected during the screening process. In addition, in the absence of specific arrangements, neither the sponsor nor PPD is financially responsible for further treatment of the subject's disease.

10.3 Investigator Documentation

Prior to beginning the study, the investigator will be asked to comply with ICH E6(R2) 8.2 and Title 21 of the CFR by providing the following essential documents, including but not limited to:

- IRB/IEC approval
- Original investigator-signed investigator agreement page of the protocol
- Form FDA 1572, fully executed, and all updates on a new fully executed Form FDA 1572
- Curriculum vitae for the investigator and each subinvestigator listed on Form FDA 1572
- Financial disclosure information to allow the sponsor to submit complete and accurate certification or disclosure statements required under 21 CFR 54. In addition, the investigators must provide to the sponsor a commitment to promptly update this information if any relevant changes occur during the course of the investigation and for 1 year after the completion of the study.
- IRB/IEC-approved informed consent, samples of site advertisements for recruitment for this study, and any other written information regarding this study that is to be provided to the subject or legal guardian, and
- Laboratory certifications and normal ranges for any local laboratories used by the site, in accordance with 42 CFR 493.

10.4 Study Conduct

The investigator agrees that the study will be conducted according to the principles of ICH E6(R2). The investigator will conduct all aspects of this study in accordance with all national, state, and local laws or regulations. Study information from this protocol will be posted on publicly available clinical trial registers before enrollment of subjects begins.

10.5 Adherence to Protocol

The investigator agrees to conduct the study as outlined in this protocol in accordance with ICH E6(R2) and all applicable guidelines and regulations.

10.6 Adverse Events and Study Report Requirements

By participating in this study, the investigator agrees to submit reports of SAEs according to the timeline and method outlined in the protocol. In addition, the investigator agrees to submit annual reports to the study site IRB/IEC as appropriate.

10.7 Investigator's Final Report

Upon completion of the study, the investigator, where applicable, should inform the institution; the investigator/institution should provide the IRB/IEC with a summary of the study's outcome and the sponsor and regulatory authority(ies) with any reports required.

10.8 Records Retention

Essential documents should be retained until at least 2 years after the last approval of a marketing application in an ICH region and until there are no pending or contemplated marketing applications in an ICH region or at least 2 years have elapsed since the formal discontinuation of clinical development of the investigational product. These documents should be retained for a longer period; however, if required by the applicable regulatory requirements or by an agreement with the sponsor. It is the responsibility of the sponsor to inform the investigator/institution as to when these documents no longer need to be retained.

10.9 Publications

After completion of the study, the data may be considered for reporting at a scientific meeting or for publication in a scientific journal. In these cases, the sponsor will be responsible for these activities and will work with the investigators to determine how the manuscript is written and edited, the number and order of authors, the publication to which it will be submitted, and other related issues. The sponsor has final approval authority over all such issues.

Data are the property of the sponsor and cannot be published without prior authorization from the sponsor, but data and publication thereof will not be unduly withheld.

11 Study Management

11.1 Monitoring

11.1.1 External Data Monitoring Committee

An independent DMC appointed by the Sponsor will review the interim safety and PK data of the first 5 subjects enrolled in the safety run-in period (See [Section 7.7.8](#)). Further details will be provided in the DMC charter.

11.1.2 Monitoring of the Study

The clinical monitor, as a representative of the sponsor, has the obligation to follow the study closely. In doing so, the monitor will visit the investigator and study site at periodic intervals, in addition to maintaining necessary telephone and letter contact. The monitor will maintain current personal knowledge of the study through observation, review of study records and source documentation, and discussion of the conduct of the study with the investigator and personnel.

All aspects of the study will be carefully monitored, by the sponsor or its designee, for compliance with applicable government regulation with respect to current GCP and current standard operating procedures.

11.1.3 Inspection of Records

Investigators and institutions involved in the study will permit study-related monitoring, audits, IRB/IEC review, and regulatory inspections by providing direct access to all study records. In the event of an audit, the investigator agrees to allow the sponsor, representatives of the sponsor, or a regulatory agency (eg, FDA) access to all study records.

The investigator should promptly notify the sponsor and PPD of any audits scheduled by any regulatory authorities and promptly forward copies of any audit reports received to the sponsor.

11.2 Management of Protocol Amendments and Deviations

11.2.1 Modification of the Protocol

Any changes in this research activity, except those necessary to remove an apparent, immediate hazard to the subject, must be reviewed and approved by the sponsor or its designee. Amendments to the protocol must be submitted in writing to the investigator's IRB/IEC for approval before subjects can be enrolled into an amended protocol.

11.2.2 Protocol Deviations

The investigator or designee must document and explain in the subject's source documentation any deviation from the approved protocol. The investigator may implement a deviation from, or a change of, the protocol to eliminate an immediate hazard to study subjects without prior IRB/IEC approval. As soon as possible after such an occurrence, the implemented deviation or change, the reasons for it, and any proposed protocol amendments should be submitted to the IRB/IEC for review and approval, to the sponsor for agreement, and to the regulatory authorities, if required.

A deviation from the protocol is an unintended or unanticipated departure from the procedures or processes approved by the sponsor and the IRB/IEC and agreed to by the investigator. A significant deviation occurs when there is nonadherence to the protocol by the subject or investigator that results in a significant, additional risk to the subject. Significant deviations can include nonadherence to inclusion or exclusion criteria, or nonadherence to FDA regulations or ICH GCP guidelines, and will lead to the subject being withdrawn from the study ([Section 4.2](#)).

Protocol deviations will be documented by the clinical monitor throughout the course of monitoring visits. Principal investigators will be notified in writing by the monitor of deviations. The IRB/IEC should be notified of all protocol deviations in a timely manner.

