1.4 Placebo Rationale

The proposed study is a double-blind, placebo-controlled, randomized trial of two doses of oral SKI-O-703 for patients with persistent and chronic ITP. Subjects will be allowed to receive stable doses of background medications including corticosteroids and immunosuppressive drugs, in line with the current standard of care. Any subject who cannot adhere to the protocol or who discontinues treatment will have an end-of-treatment visit and will be followed for the intended duration of the study.

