4.2 Withdrawal of Subjects From Study Drug and/or the Study

The duration of the study is defined for each subject as the date signed informed consent is provided through date of the last follow-up visit on Week 16.

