4.2.1 Reasons for Withdrawal/Discontinuation

Subjects may withdraw from the study at any time and for any reason without prejudice to their future medical care by the investigator or at the study site. Every effort should be made to keep subjects in the study. The reasons for subjects not completing the study will be recorded. A subject may be withdrawn from the study for any of the following reasons:

1. Noncompliance with the protocol
2. A serious or intolerable adverse event(s) (AE[s]) that in the investigator's opinion requires withdrawal from the study
3. Central nervous system bleeding or life-threatening gastro-intestinal bleeding. Please also refer to the additional information in the 'Note' at the bottom of this section.
4. Laboratory safety results that reveal clinically significant hematological or biochemical changes from the baseline values
5. Symptoms of an intercurrent illness not consistent with the protocol requirements or that justify withdrawal
6. Lost to follow-up. Subjects that are considered lost to follow-up, reasonable attempts must be made to obtain information on the final status of the subject. At a minimum, 2 phone calls must be made and 1 certified letter must be sent for documentation
7. Other reasons (eg, pregnancy, development of contraindications of use of study drug, breakthrough bleeding)

8. The subject withdraws consent or the investigator or sponsor decides to discontinue the subject's participation in the study
9. Death of the subject.

Note: Bleeding events in the ITP studies are common during the first few weeks of the study before the drug has a chance to take effect; hence, all the bleeding events in this study should be recorded as an AE or SAE (based on seriousness criteria). These events should not result in removal of the subjects from the study, at least during the first 4 weeks of treatment. As the standard of care among the participating countries may differ, platelet transfusions are allowed as a rescue therapy for such events; however, these therapies may be reserved for serious or life-threatening bleeding events.

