4.2.2 Handling of Withdrawals

Subjects are free to withdraw from the study or study drug at any time upon request. Subject participation in the study may be stopped at any time at the discretion of the investigator or at the request of the sponsor.

Subjects who discontinue study drug or active participation in the study will no longer receive study drug. When a subject withdraws from the study drug or active participation in the study, the reason(s) for withdrawal shall be recorded by the investigator on the relevant page of the electronic case report form (eCRF). Whenever possible, all subjects who discontinue study drug permanently or withdraw from the study prematurely will undergo all end-of-study assessments. Subjects who fail to return for final assessments will be contacted by the site in an attempt to have them comply with the protocol. Following a minimum of 2 documented unsuccessful telephone calls, a registered letter will be sent to the subject in a final attempt to ensure protocol compliance.

It is vital to obtain follow-up data on any subject withdrawn because of an AE or SAE. In every case, efforts must be made to undertake protocol-specified safety follow-up procedures.

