4.2.3 Replacements

Subjects who are randomly assigned and not dosed will be replaced. Subjects who discontinue the study for any reason after dosing will not be replaced.

5 Study drugs

Two dose levels of SKI-O-703 will be evaluated: 200 mg BID and 400 mg BID. The SKI-O-703 capsules will contain 100 mg of drug substance. Placebo capsules are filled with microcrystalline cellulose.

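### Protocol 4.2.2 schedules no platelet counts for patients who stop study drug, and 11.2.2 adds mandatory study withdrawal for risk-related deviations, although Section 1.4 and the SAP call for follow-up and data to Week 12

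*Protocol*

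**What the plan says.** **Handling of discontinuation.** Protocol 4.2.2 says that, whenever possible, "all subjects who discontinue study drug permanently or withdraw from the study prematurely will undergo all end-of-study assessments". It does not separate stopping drug from leaving the study, and it names no platelet counts between stopping and those assessments. For patients withdrawn because of an adverse event it adds: "In every case, efforts must be made to undertake protocol-specified safety follow-up procedures".

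**Deviations.** Protocol 11.2.2 calls a deviation significant when non-adherence "results in a significant, additional risk to the subject". Such deviations can include breaches of eligibility criteria, and they "will lead to the subject being withdrawn from the study". The section refers back to 4.2, headed "Withdrawal of Subjects From Study Drug and/or the Study". Under that heading, 4.2.1 is permissive: "A subject may be withdrawn from the study for any of the following reasons", with non-compliance first on the list.

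**Follow-up commitment.** Protocol 1.4 says that a patient who cannot adhere or who discontinues treatment "will have an end-of-treatment visit and will be followed for the intended duration of the study".

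**Replacement and analysis set.** Protocol 4.2.3: "Subjects who discontinue the study for any reason after dosing will not be replaced". Under SAP 4.6.2 a dosed patient with one post-baseline platelet count belongs to the ITT set.

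**Analyses.** The treatment-policy sensitivity analysis of the primary endpoint (SAP 8.1.2) and the main and treatment-policy analyses of change from baseline (SAP 8.2.2) all run to Week 12 irrespective of rescue or discontinuation.

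**The concern.** The SAP's treatment-policy analyses ask what happened to patients as randomised, including after they stopped drug. That needs counts taken off drug. Section 1.4 promises follow-up, but the operational sections do not carry it out. A site working from 4.2.2 and Table 2 has no instruction to keep drawing counts: the columns before follow-up are headed as on-treatment visits, and a footnote asks for the Week 12 visit while the patient is still on therapy.

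Stopping drug alone is foreseen. Protocol Table 1 requires permanent discontinuation for a second liver-enzyme, neutrophil, blood-pressure or nausea/vomiting event, and for QTcF prolongation that persists. These patients have not withdrawn consent, and their counts could be collected. If sites read the text differently, some will collect them and some will not. A count not taken cannot be recovered at the analysis stage.

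**Working it through.** The documents give no discontinuation rate and no figure on this point, so there is no stated number to reproduce. The check compares the texts and counts visits.

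**1. Texts side by side**

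| Situation | 1.4 | 4.2.1 / 4.2.2 | 11.2.2 |
|---|---|---|---|
| Stops drug only | End-of-treatment visit, then followed for planned duration | End-of-study assessments, whenever possible | Not addressed |
| Deviation with significant added risk | Followed, if the patient cannot adhere | Withdrawal may follow | Withdrawal from the study will follow |

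Section 4.2 covers both stopping drug and leaving the study, but does not say which of the two a significant deviation triggers. The cross-reference therefore does not settle the matter.

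**2. Scheduled counts per patient**

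The hematology row of Protocol Table 2, after Day 1 and up to Week 12, gives Day 4, Day 8 and Weeks 3, 5, 7, 9, 11 and 12: 8 counts. Values to impute = scheduled counts after the last one attended.

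| Stops after | Scheduled values missing | Share |
|---|---|---|
| Day 8 | Weeks 3, 5, 7, 9, 11, 12 = 6 | 6/8 = 75% |
| Week 3 | 5 | 5/8 = 62.5% |
| Week 7 | 3 | 3/8 = 37.5% |
| Week 9 | 2 | 2/8 = 25% |

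Table 2 also provides one early-withdrawal count. SAP 4.3 assigns no visit windows, so no rule places that count at a scheduled visit. If it were allowed to stand for one, each number falls by 1: 5/8, 4/8, 2/8 and 1/8.

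**3. Trial scale**

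Total scheduled counts = 60 × 8 = 480. One patient stopping after Day 8 accounts for 6/480 = 1.25% of them. By arm, that is 6/(24 × 8) = 6/192 = 3.1% in an active arm and 6/(12 × 8) = 6/96 = 6.25% on placebo. The number of such patients is an assumption. With 1 to 3 patients whose counts could have been collected, stopping between Week 7 and Day 8, the range is 1 × 3 = 3 to 3 × 6 = 18 of 480, or 0.6% to 3.75%. It scales in proportion to the number of patients.

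**4. Effect by analysis, for a stop after Day 8**

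- *Primary response rate (SAP 8.1.1).* Response at any one visit suffices, so a patient who has already responded remains a responder. An undetermined response is counted as non-response. Only a first response arising after drug was stopped could be missed. I give no figure, because that loss cannot be separated from the effect of stopping drug.
- *Treatment-policy sensitivity analysis (SAP 8.1.2).* Six of eight values are imputed under missing at random, using treatment, baseline, previous visits and prior TPO-receptor agonist use. Discontinuation is not among the predictors. With few off-drug counts observed, the imputed values lean on patients still taking drug.
- *Change from baseline, main analysis (SAP 8.2.2).* This uses observed data. The last two counts are Day 8 plus the early-withdrawal count, or Day 4 and Day 8 if that count is not used. Either way they come from about Week 2 rather than Weeks 11 and 12.

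**The case against.** The strongest reply is that the texts can be reconciled. Table 2 labels the Week 16 visit as the end of study, so 4.2.2 could mean an end-of-treatment visit, follow-up, and then the Week 16 assessments. Section 1.4 is one sentence of placebo rationale and does not mention platelet counts. This stands in part: the reading is possible, but even then nothing names counts between stopping drug and Week 16.

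Second, the SAP plans for missing data. SAP 8.2.1 excludes visits with missing results and treats undetermined achievement as non-response. SAP 8.2.2 includes imputation under missing at random and a control-based version under missing not at random. This also stands in part. The control-based analysis belongs to the hypothetical strategy for change from baseline. The treatment-policy analysis of the primary endpoint has only the missing-at-random version, and imputed values do not replace counts that could have been taken.

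Three stronger readings are tempting, and the documents support none of them:

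- A reader might infer that 4.2.2 forbids or ends platelet counts. It neither limits patients to end-of-study assessments nor bars later counts. It simply schedules none.
- A reader might infer that any deviation removes a patient. Section 11.2.2 is confined to significant added risk and can be read as a safety exception to 1.4, although the protocol does not say so.
- A reader might infer that the primary result, the arm comparison or safety follow-up is compromised. The primary endpoint depends little on late counts, and no difference in loss between arms is shown. Safety follow-up is partly protected by 4.2.2, by 6.4.5.9 and by the early-withdrawal visit.

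**Conclusion.** The inconsistency is real in the current text, and 4.2.2 is its main source because it covers drug-only discontinuation. Section 11.2.2 is a narrower contributor, and amending it alone would not bring the counts back.

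The consequence is confined to the treatment-policy sensitivity analysis and to endpoints that depend on late counts, chiefly change from baseline. Per affected patient it ranges from 2 of 8 scheduled values (stop after Week 9) to 6 of 8 (stop after Day 8), before any credit for an early-withdrawal count. Across the trial the size is unknown, because the documents give no frequency; the 0.6% to 3.75% above is an illustration resting on an assumed 1 to 3 patients. A total discontinuation rate would overstate the recoverable loss, since no amendment brings back counts after death, consent withdrawal or loss to follow-up. I give no shift in arm means: the documents offer no figure for how far an early pair of counts differs from a Week 11 and 12 pair.

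This is worth correcting as a cheap improvement. It is not a threat to the primary conclusion.

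**What to change.** - **Protocol 4.2.2:** separate stopping drug from leaving the study. Patients off drug who have not withdrawn consent continue the scheduled platelet counts, and the bleeding and rescue records, through Weeks 12 and 16, as 1.4 implies. Align the Table 2 column heading and the Week 12 footnote with this.
- **Protocol 11.2.2:** a significant deviation leads to stopping study drug where safety requires it. It leads to study withdrawal only if consent is withdrawn or was never valid, or if the visits themselves carry the risk.
- **Analysis:** handle the deviation through the per-protocol set (SAP 4.6.3).

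The cost is a few sentences in the next amendment. The downside is that a few off-drug patients attend visits already in the schedule, and sites must check whether an exception applies, mainly the validity of consent.

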11.3 Study Termination

Although Oscotec Inc. has every intention of completing the study, Oscotec Inc. reserves the right to discontinue the study at any time for clinical or administrative reasons which may include (but not limited to) the followings:

- Unacceptable risk to a subject participating in the study
- The decision on the Sponsor to suspend or discontinue evaluation of the study drug
- Insufficient adherence to protocol
- Failure to comply with regulation, etc.

The end of the study is defined as the date on which the last subject completes the last visit (includes follow-up visit).

## List of Abbreviations

Abbreviation	Definition
AE	adverse event
AESI	adverse event of special interest
ANCOVA	analysis of covariance
ATC	Anatomical Therapeutic Chemical
AUC	area under the concentration versus time curve
AUC 0-tau	area under the plasma concentration-time curve within a dosing interval
AUEC	area under the effect versus time curve
AUEC 0-tau	area under the effect versus time curve within a dosing interval
BID	twice daily
BLQ	below the limit of quantification
BMI	body mass index
CI	confidence interval
CL/F	apparent oral clearance
C max	maximum observed concentration
eCRF	electronic case report form
CTCAE	Common Terminology Criteria for Adverse Events
C trough	trough concentration observed at steady state
CV	coefficient of variation
ECG	electrocardiogram
EOT	end-of-treatment
ITP	immune thrombocytopenia
ITT	Intend to treat
IVRS	interactive voice response system
K el	terminal phase elimination rate constant
K el lower	lower bound used for the estimation of K el
K el upper	upper bound used for the estimation of K el
K-M	Kaplan-Meier
LS	least-square
MedDRA	Medical Dictionary for Regulatory Activities
ORR	overall platelet response rate
PD	pharmacodynamic(s)
PK	pharmacokinetic(s)
PP	per protocol
PT	preferred term
QTcF	corrected QT interval by Fridericia formula
R AUC	accumulation ratio

Abbreviation	Definition
R met	metabolite ratio
Rsq (r  )	coefficient of determination
SAE	serious adverse event
SAP	statistical analysis plan
SD	standard deviation
SE	standard error
SOC	system organ class
t 1/2	apparent terminal elimination half-life
t 1/2,eff	effective half-life
TEAE	treatment-emergent adverse event
TE max	Time to achieve maximum effect
T max	time to reach maximum observed concentration
V z /F	apparent volume of distribution
WHODD	World Health Organization Drug Dictionary

